4. Parenteral nutrition will be provided as outlined in the standard NICU feeding protocol and will be consistent with parenteral intake provided to all VLBW infants in the NICU regardless of study participation.
5. Enfamil HP HMF will be added to provide 22 calories/ounce on the initiation of enteral feeds for the intervention group (feeding day 1). For the control group, Enfamil HP HMF will be added to provide 22 calories/ounce when enteral feeding volume reaches 80 mL/kg/day (feeding day 8). Caloric density will be advanced to 24 calories/ounce at feeding day 10 for both groups. The caloric density progression follows the standard NICU fortification practices.

Blinding Procedures

Feeding tolerance is largely subjective. As an important secondary outcome, we will blind all healthcare personnel to study group allocation for the first 7 feeding days.

1. Upon consent, participants will be randomized to one of two study groups.
2. The milk bank in the NICU is responsible for all human milk preparation. Milk bank technicians will receive the group allocation for each participant and prepare human milk with/without fortification according to standard formulations.
3. Group allocation for each participant will be recorded by milk bank technicians on the daily feeding sheets (standard procedures for all infants). Group allocation and fortification will be confirmed by one study member of the study team who will be unblinded (co-Investigator [name] who is the NICU dietitian that oversees the milk laboratory).
4. Blinding will be accomplished by removing the caloric content from the label for all study participant. In the field that contains calories, “study participant” will be entered. Blinding will occur during the first 7 feeding days and calorie content will be recorded on feeding day 8 and all subsequent feeding days.

Intervention Group

	Parenteral Nutrition/IV Fluids				Enteral Feedings Given by 30-60 minute bolus q 3 hours NG/OG		Intervention Group
Feeding Day	Glucose mg/kg/min	Protein, g/kg	Lipids, g/kg	IVF, mL/kg	Enteral Feedings, mL/kg	Feeding Type	Notes
Day 1	6-10	3.5-4	3	80-130	20	Human Milk +HP HMF	Add Enfamil High Protein Human Milk Fortifier to 22 calories
Day 2	6-10	4	3	80-130	20	Human Milk +HP HMF	
Day 3	6-10	4	3	90-110	40	Human Milk +HP HMF	
Day 4	6-10	4	3	90-110	40	Human Milk +HP HMF	
Day 5	6-10	4	3	70-90	60	Human Milk +HP HMF	
Day 6	6-10	3-4	3	70-90	60	Human Milk +HP HMF	
Day 7	6-10	2.5-4	2	50-70	80	Human Milk +HP HMF	

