Briefly describe the actual source records or measures that will be used to collect data about participants. (All surveys, interview scripts, and data collection forms will be attached elsewhere in the application. Do not add other documents to the protocol.) Describe what data will be collected and how it will be collected at all measurement/data collection time-points.

Data will be collected from the patient's EMR. Data to be collected include: date of birth, gender, estimated gestation age (EGA), Apgar score at 1 and 5 minutes, weights, head circumference, length, z-scores for weight, length, and head circumference, total volume of feeds and TPN, number of missed enteral feeds, maternal milk vs donor milk volumes. Laboratory data including basic metabolic panel, magnesium, phosphorus, alkaline phosphatase and urine sodium, potassium and magnesium will be collected on day 22 as per the current standard of care. No blood collections or other procedures will be performed specifically for the study. Clinical outcomes will be collected to include: incidence of metabolic acidosis, NEC, oxygen requirement at 36 weeks, PDA, and death.

Anthropometrics

Anthropometrics are measured as part of the standard physical assessment of the preterm infant. For this study, all anthropometric measurements and calculations will follow AU's standard preterm infant physical assessment guidelines.

Weight

1. Body weight will be measured within 24 hours of birth and then every 7 days until 28 days of life and again at 36 weeks post-menstrual age (PMA).
2. Measurement of weight will be performed by the principal investigator (PI) and/or co-Investigators
3. Weight will be measured (x 2) on a tared infant scale calibrated to the nearest 10 grams. Weights will be recorded in grams (g). Discrepancies of greater than 20g will be repeated.
4. Infants will be weighed without a diaper.
5. Average weight will be recorded in the EMR and documented in the database.
6. Weight will be plotted on a gender-specific Fenton growth chart in the EMR and the percentile recorded in the database

Weight Gain

1. Weight gain and growth velocity (GV) will be calculated at 28 days of life and 36 weeks PMA.
2. Weight gain will be recorded as g/day
3. GV will be calculated as follows and recorded in the database:

$$GV \text{ (g/kg/day)} = \frac{[1000 \times (Wn - W1)]}{(Dn - D1) \times \left[\frac{Wn + W1}{2} \right]}$$

W= weight in grams

D = day

1 = interval of time chosen

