n= the end of the interval of time chosen

Head Circumference

1. Head circumference will be measured within 24 hours of birth (x 3) and then every 7 days until 28 days of life and again at 36 weeks PMA. Discrepancies of greater than 0.5cm will be repeated.
2. Measurement of head circumference will be performed by the principal investigator (PI) and/or co-Investigators
3. Head circumference will be measured with a Seca® non-stretch, Teflon® measuring tape.
4. The tape will be applied firmly around the head above the supraorbital ridges, covering the most prominent part of the frontal bulge anteriorly, and over the part of the occiput that gives the maximum circumference.
5. The greatest of three measurements will be recorded in centimeters (cm) and average recorded.
6. Measurements will be recorded in the EMR and documented in the database.

Length

1. Body length will be measured within 24 hours of birth (x 2) and then every 7 days until 28 days of life and again at 36 weeks PMA.
2. Length will be measured on a length board with a stationary head piece and adjustable foot piece.
7. Measurement of length will be performed by the principal investigator (PI) and/or co-Investigators
3. One examiner will hold the infant's head with the Frankfurt plane in the vertical position and apply gentle traction to bring the top of the head into contact with the fixed headboard. The second examiner will hold the infant's feet, toes pointing directly upward, and also applying gentle traction to bring the movable footboard to rest firmly against the infant's heels.
4. The average of two measurements, agreeing within 0.4 cm, will be recorded.
5. Measurements will be recorded in the EMR and documented in the database.

Z-scores

1. Z-scores for weight, length, and head circumference will be retrieved from the EMR. Z-scores will be calculated at 28 days of life and 36 weeks PMA.
2. Z-scores are calculated by Cerner® (Cerner®, North Kansas City, MO) and recorded on the Fenton growth curve in the EMR

Mother's Milk Collection

1. Mother's milk collection will follow standard NICU milk collection procedures: All study participants will be provided with:
 - a. Instructions for milk collection, written and verbal
 - b. Access to a hospital grade electric breast pump, individual pump kit, and a comfortable place to express

- c. A manual breast pump will be provided upon request
- d. Sterile, single-use breastmilk collection containers

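### One co-investigator is unblinded but not barred from measuring outcomes, feeding sheets that carry allocation have no stated access limit, and blinding is promised only for feeding days 1-7

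*Protocol*

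**What the plan says.** All of this stands in section 8b of the Protocol.

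- **Scope of blinding** (Blinding Procedures, opening). The stated motive is that feeding tolerance is subjective. The promise is: "we will blind all healthcare personnel to study group allocation for the first 7 feeding days".
- **Who is unblinded** (Blinding Procedures, item 3): "Group allocation and fortification will be confirmed by one study member of the study team who will be unblinded". This is a co-investigator "who is the NICU dietitian that oversees the milk laboratory". The milk bank technicians also receive the allocation.
- **Where allocation is written** (same item): "Group allocation for each participant will be recorded by milk bank technicians on the daily feeding sheets (standard procedures for all infants").
- **Masking device and its end** (item 4). Calories are left off the label, then: "Blinding will occur during the first 7 feeding days and calorie content will be recorded on feeding day 8 and all subsequent feeding days".
- **Who measures.** Weight: "Measurement of weight will be performed by the principal investigator (PI) and/or co-Investigators". Head circumference: "Measurement of head circumference will be performed by the principal investigator (PI) and/or co-Investigators". Length: "Measurement of length will be performed by the principal investigator (PI) and/or co-Investigators". None of the three sections excludes the unblinded co-investigator.
- **When the primary outcome is measured** (section 1). Weight growth velocity at 28 days of life.

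**The concern.** Three gaps meet at the outcome measurement.

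1. The rules on who measures and on who is unblinded overlap in one person. As written, someone who knows the arm may take the weight that determines the primary outcome.
2. The label is masked, yet the arm itself is entered on a document kept for every infant. Nothing says who may read it.
3. No commitment covers the day-28 measurement, or the one at 36 weeks post-menstrual age.

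The exposure differs by outcome. Weight comes off a scale and is the best protected. Length depends on traction applied by two examiners, and head circumference on where and how firmly a tape is placed. Feeding tolerance is subjective by the Protocol's own account, and volumes and caloric density keep rising after feeding day 7. Tolerance judgements can also reach the analysis: feed interruptions are an ANCOVA covariate (section 9a), and one withdrawal criterion rests on the attending neonatologist's opinion (section 11a).

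**Working it through.** **Scale of the design.** Section 9b assumes means of 10.56 and 13.56, SD 3.64, two-sided alpha 0.05 and 80% power. The two-sample t-test calculation gives 24.1, rounded up to 25 per group, which matches the Protocol. The design difference is 13.56 - 10.56 = 3.00 g/kg/day. This serves only as a yardstick; the sample size is not in dispute.

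**Time from the end of promised blinding to day 28.** Count birth as day of life 1 and let feeding day 1 fall on day of life f. Feeding day 7 is then day f + 6, and the gap is 28 - (f + 6) = 22 - f days.

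| Start of feeds | f | Last blinded day of life | Gap to day 28 |
|---|---|---|---|
| Day of birth | 1 | 7 | 21 days |
| Up to about 48 h (usual, section 8a) | 2 to 3 | 8 to 9 | 20 to 19 days |
| 96 h (latest allowed, section 3) | 5 | 11 | 17 days |

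**Effect of a weighing error on growth velocity (GV).** The Weight Gain formula is GV = 1000 × (Wn - W1) / [(Dn - D1) × (Wn + W1)/2]. Assume W1 = 1250 g, Wn = 1650 g and 28 days; these weights are mine, not the Protocol's.

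- True reading: 1000 × 400 / (28 × 1450) = 9.85.
- One of two readings 20 g high, so the recorded average is 10 g high: 1000 × 410 / (28 × 1455) = 10.06. Shift 0.21, or 0.21/3.00 = 7% of the design difference.
- Recorded average itself 20 g high: 1000 × 420 / (28 × 1460) = 10.27. Shift 0.42, or 0.42/3.00 = 14%.

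For birth weights of 1000 to 1500 g, a true GV of 10.56 and intervals of 27 to 28 days, a 10 g error in the recorded average shifts GV by 0.17 to 0.27, and a 20 g error by 0.34 to 0.54.

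**Effect on the test.** Suppose every infant in one arm, and none in the other, carried the shift b. With 25 per group the noncentrality is b / (3.64 × √(2/25)). For b = 0.21 it is 0.204 and the two-sided error rate rises from 5% to 5.5%. For b = 0.42 it is 0.408 and the rate is 6.9%. One possible measurer among several would produce less.

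**Does the label reveal the arm after feeding day 7?** On schedule, no. Both arms are planned at 22 calories/ounce on feeding day 8 and 24 on feeding day 10. The routes that remain are the unblinded co-investigator, the feeding sheets, and the absence of any commitment after feeding day 7.

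**The case against.** The case on the other side has real force. Weight is taken twice on a tared, calibrated scale without a diaper, the average is recorded, and a gap above 20 g triggers a repeat by rule. That leaves little room for an observer. Length needs two examiners and two averaged readings that agree within 0.4 cm. Blinding was introduced for a limited purpose, feeding tolerance in the week when the arms differ, and the Protocol met that purpose in its own terms. Most withdrawal criteria do not turn on anyone's opinion of the arm. All of this stands, and it keeps the point modest.

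A reader might infer more than the text supports:

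- *That the dietitian will measure outcomes.* The Protocol permits this; it does not say it.
- *That bedside staff or measurers read the allocation on the feeding sheets.* Access is not described, either as open or as restricted.
- *That showing calories from feeding day 8 unblinds the trial.* It does not for infants on schedule, and no disclosure of allocation is planned. What is missing is a promise.
- *That weighing leaves discretion over repeats, or that 14% of the design difference is the bias to expect.* The repeat rule is fixed. The 20 g is a tolerance between two readings, not an error in the recorded average.

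The objection does not remove the overlap between the unblinded role and the measuring role, or the lack of assessor blinding at day 28.

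**Conclusion.** The point holds as a gap in the plan, not as a demonstrated breach of blinding. An unblinded co-investigator may take the primary-outcome weight. Allocation goes on routine sheets with no stated access limit although all healthcare personnel are to be blinded. The blinding commitment ends 17 to 21 days before the day-28 measurement.

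For the primary outcome the likely bias is small: about 0.21 g/kg/day if one reading is 20 g off, with 0.42 as a worst case, against a design difference of 3.00. Those figures rest on the assumed weights of 1250 g and 1650 g. The error rates of 5.5% and 6.9% further assume that a whole arm is shifted one way, so they are ceilings. Length, head circumference and feeding-tolerance judgements are more exposed, but the documents give no basis for putting a size on that. The change is worth making because it costs very little.

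**What to change.** 1. State in the Weight, Head Circumference and Length sections that the unblinded co-investigator takes no anthropometric measurements.
2. Keep allocation in a milk-lab record that measurers and bedside staff cannot access. On any sheet they do see, use the same study-participant entry as on the label.
3. State that allocation stays concealed from measurers until the day-28 measurement and, as far as the feeding schedule allows, from the clinical team as well.

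The cost is wording, one restricted record and one fewer possible measurer. For infants off the planned schedule, the calorie label may also need masking for longer: the control arm's start is tied to enteral volume as well as to feeding day 8, so a delayed infant's label could differ between arms. Feeding, sample size and analysis are unchanged.

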To examine differences between the two groups and assess for potential confounding variables two-sample t-tests will be used for continuous variables, chi-square tests will be used for categorical variables, and Wilcoxon Rank Sum tests will be used for ordinal data. Variables that will be examined include all collected EMR data (e.g., demographics, feeding related, laboratory, and clinical measures) and anthropometric measures.

To examine differences between the two groups (day 1 vs. day 8), a simple two-sided two-sample t-test will be used as a preliminary test for differences in continuous outcomes (e.g., weight growth velocity, head circumference growth velocity, length growth velocity, zscores). Then, to control for various potential confounders or covariates, analysis of covariance (ANCOVA) will be used with the main effect of interest being the group effect. Covariates that will be adjusted for include gestational age, total number of feed interruptions, incidence of metabolic acidosis, and NEC. Because there are only two groups, no adjustment to the overall alpha level will be needed to control for multiple comparisons.

b. When applicable, provide a power analysis:

N/A

The sample size was determined assuming an alpha level of 0.05, power of 80%, a common standard deviation of 3.64, and a two-sided two-sample t-test to examine differences in weight growth velocity at 28days between the two feeding protocol groups. The mean for the standard of care group (fortification beginning on day 8) was 10.6% and for the intervention group (fortification beginning on day 1) was 12.3, 12.6 and 13.6. The sample size required for each mean difference is below

Assumed Mean in Each Group		Sample Size per Group
Fortification Day 8	Fortification Day 1	
10.56	12.25	74
10.56	12.56	53
10.56	13.56	25

A sample size of 25 per group, for a total of 50 subjects will be needed.

c. Describe how data and specimens will be handled:
 
Data will be collected and recorded on a coded spreadsheet that is stored on a research specific Box drive assigned by AU IRB.
	 N/A

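### Z-scores are compared at day 28 and 36 weeks PMA without using the birth z-score, which costs precision with 25 infants per arm although the birth measurements exist

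*Protocol*

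**What the plan says.** Protocol section 8, under Z-scores, fixes the time points: "Z-scores will be calculated at 28 days of life and 36 weeks PMA". The general list of data items in the same section includes "z-scores for weight, length, and head circumference" with no time point attached.

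Section 9a places z-scores among the "continuous outcomes (e.g., weight growth velocity, head circumference growth velocity, length growth velocity, zscores" and gives two analyses: an unadjusted two-sided t-test, then ANCOVA. On the latter it states: "Covariates that will be adjusted for include gestational age, total number of feed interruptions, incidence of metabolic acidosis, and NEC". No birth z-score, birth weight or change in z-score from birth appears there.

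The baseline measurements exist. For weight, section 8 says: "Body weight will be measured within 24 hours of birth and then every 7 days until 28 days of life". Length and head circumference are also taken within 24 hours of birth. For weight, the Fenton percentile goes into the database as well.

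Section 3 admits birth weights of 1000-1500 g, excludes infants below the 3rd Fenton percentile and sets no gestational age limit. Section 1 makes growth velocity at 28 days the primary outcome, and section 4 sets 25 infants per group.

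**The concern.** A z-score at day 28 or 36 weeks PMA reflects both where the infant started and what happened afterwards. Feeding can change only the second part. Under the eligibility rules infants can enter anywhere from the 3rd percentile upward, so size for age at birth will vary between them. An analysis that ignores the starting point leaves that variation in the error term. It also lets part of any chance difference in birth size between two arms of 25 pass into the estimated effect.

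At stake are three growth outcomes (weight, length and head circumference z-scores, each at two time points) in a trial of 50 infants. An effect could be missed, or an estimate shifted by chance, when the variable that would reduce both risks is already being measured.

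**Working it through.** **The plan's own figure.** Section 4 gives 74, 53 and 25 per group for a growth velocity of 10.56 against 12.25, 12.56 and 13.56, with SD 3.64, 80% power and two-sided alpha 0.05. The exact two-sample t calculation gives 73.8, 53.0 and 24.1, which round up to 74, 53 and 25. The figures reproduce. They concern growth velocity; the protocol gives no power statement for z-scores.

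**Inputs for the z-score question.** From the protocol: n = 25 per arm, 1:1 randomisation, and the ANCOVA covariates of section 9a. Assumed, because the protocol gives no value: a correlation r between birth and later z-score of 0.7 to 0.9, with equal SDs at both times. The later z-score is scaled to SD 1.

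**1. Bias.** In 20,000 simulated trials at each of r = 0.5, 0.7 and 0.9, with a true difference of 0.50, the unadjusted comparison gave a mean estimate of 0.50. Type I error was 4.9% to 5.3%. There is no bias to correct.

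**2. Chance imbalance.** The standard error of the difference in mean birth z is sqrt(2/25) = 0.28 SD, so the 95% range is ±1.96 × 0.283 = ±0.55 SD. On average a fraction r of any imbalance carries into the unadjusted difference.

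**3. Gain against the unadjusted t-test.** With birth z as covariate the residual SD is sqrt(1 − r²). The detectable difference is for 80% power; unadjusted it is 0.81 SD.

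| r | 1 − r² | SE relative to t-test | Detectable difference (SD) | Power for a true 0.5 SD |
|---|---|---|---|---|
| unadjusted | 1 | 100% | 0.81 | 41% |
| 0.7 | 0.51 | 71% | 0.58 | 68% |
| 0.8 | 0.36 | 60% | 0.49 | 82% |
| 0.9 | 0.19 | 44% | 0.35 | 98% |

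At r = 0.5 the detectable difference would be 0.70 SD and the power 52%.

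**4. Gain against the planned ANCOVA, weight only.** Gestational age is already a covariate. With birth weight held to 1000-1500 g, more mature infants tend to be small for age and less mature ones large for age, so gestational age carries information on birth weight z. A simulation of this window with the 3rd percentile exclusion gave a correlation ρ between gestational age and birth weight z of about −0.76 to −0.89. It assumed that median weight rises 10-16% per week, that log weight has SD 0.15-0.25, and that the gestational age mix is flat or rising.

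If gestational age acts on later weight z only through birth z, the ratio of standard errors is sqrt[(1 − r²)/(1 − r²ρ²)]:

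- r = 0.7, ρ = −0.89: sqrt(0.51/0.612) = 0.91
- r = 0.7, ρ = −0.76: sqrt(0.51/0.717) = 0.84
- r = 0.9, ρ = −0.89: sqrt(0.19/0.358) = 0.73
- r = 0.9, ρ = −0.76: sqrt(0.19/0.532) = 0.60

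Eligibility does not restrict length or head circumference directly, so gestational age should stand in less well for those birth z-scores and the gain is probably larger. This part was not quantified.

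**The case against.** The strongest reply has four parts.

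- **The trial is randomised and growth is already measured as change.** Both are true. The primary outcome is a velocity computed from a start and an end weight, and section 9a also lists length and head circumference velocities. This confines the point to precision in non-primary outcomes.
- **Gestational age is adjusted for.** This stands in part for weight, as step 4 shows. A reader might infer that gestational age cannot help because a z-score is already relative to age. That holds in an unselected population, but not within a 1000-1500 g window.
- **Section 9a screens anthropometric measures for confounding, and its covariate list says only that it includes the four named.** Neither replaces a prespecified baseline covariate. With 25 per arm, an imbalance in birth z of up to about 2.01 × 0.283 = 0.57 SD would not be significant, yet on average it would carry 0.40 to 0.51 SD into the unadjusted outcome difference at r = 0.7 to 0.9. An open list does not commit the analyst to the birth value.
- **Birth data are available, and a statistical analysis plan may settle the model.** Availability makes the change cheap but does not make it planned. The protocol has itself fixed both the time points and the named covariates.

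A reader might also infer that the z-score outcomes largely measure size at birth. The protocol does not support that. The birth z-score would have to explain more than half of the variance, which needs r above about 0.71, and no r is given. Even then, the difference between randomised arms would still estimate the effect of fortification.

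**Conclusion.** The point holds as one of efficiency. The z-score time points omit birth, and neither planned analysis uses the birth value. The comparison is valid but less precise than it need be, and it is open to chance imbalance in birth size with a standard error of 0.28 SD.

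The size of the gain rests on an assumed r of 0.7 to 0.9. For the weight comparison with the planned ANCOVA it also rests on the simulated link between gestational age and birth weight z. The standard error would fall to about 71%-44% of the unadjusted t-test's. For weight it would fall to roughly 91%-60% of the planned ANCOVA's, with probably a larger gain for length and head circumference. The primary outcome and the sample size are untouched.

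**What to change.** In section 8, add birth to the z-score time points, deriving weight, length and head circumference z-scores from the measurements already made within 24 hours. In section 9a, prespecify the matching birth z-score as an ANCOVA covariate for each z-score outcome at each time point.

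Change in z-score from birth may be reported for readability. Once birth z is in the model, change and attained value give the same group effect, so redefining the outcome gains nothing further. An unadjusted change score is not a substitute: it is noisier than ANCOVA at any of the correlations considered, and noisier than the attained value when r is below 0.5.

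The cost is one more extraction of values already measured and a small wording change in two sections. No procedure is added for the infants.
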